8.2.3 Time Period and Frequency for Event Assessment and Follow-Up

AEs and/or SAEs may come to the attention of study personnel during study follow-up phone calls, when the subject presents for office visits/medical care, or upon review of source documents by a study monitor.

All AEs, including local and systemic reactions not meeting the criteria for SAEs, will be captured on the appropriate CRF. Information to be collected includes event description, date of onset, clinician's assessment of severity, relationship to the Jewel, and resolution/stabilization of the event. All AEs occurring during the study must be documented appropriately, regardless of relationship. All AEs will be followed to adequate resolution or will be marked as ongoing at the time of study exit.

Any medical condition present at the time the subject is screened will be considered as baseline and not reported as an AE. However, if the subject's condition deteriorates at any time during the study, that condition's deterioration will be recorded as an AE.

Changes in severity of an AE will be documented to allow for an assessment of the duration of the event at each level of severity. All AEs will be characterized for severity when reported and, if ongoing, updates to the severity of any ongoing AEs will be assessed at subsequent visits.

8.2.4 Adverse Event Reporting

AEs must be documented on a CRFs by site staff. It is the responsibility of the Investigator to ensure that all information is correct. When reporting any AEs or SAEs, the following information should be included:

- Description of event (including diagnosis)
- Onset date
- Severity
- Relationship to study device
- Action taken
- Outcome
- Duration / Resolution date

8.2.5 Serious Adverse Event Reporting

All SAEs must be reported to the Sponsor within 24 hours of learning about the event, regardless of the time that may have elapsed from the time the event occurred. The Sponsor must also receive a completed AE form within three (3) working days of the site being notified of the event. Investigators shall comply with all local reporting requirements. The Sponsor will inform regulatory authorities of SAEs per local and federal requirements.

8.2.6 Unanticipated Adverse Device Effect Reporting

The Investigator shall complete an AE Form and submit it to the Sponsor and to the reviewing IRB immediately, but no later than ten (10) working days after the Investigator first learns of the effect, as required by 21 CFR §812.150. The Sponsor is responsible for conducting an evaluation of a suspected UADE, and shall report the results of such evaluation to the Food and Drug Administration (FDA) and to all other participating IRBs and Investigators within ten (10) working days after the Sponsor first receives notice from the Investigator. Thereafter, the Sponsor shall submit such additional reports concerning the effect as the FDA requests.

8.2.7 Device Deficiencies

All device deficiencies must be documented and reported to the Sponsor within three (3) days. The DSMB is also responsible for assessing whether a device deficiency poses an unreasonable risk to patients if the study is continued.

8.2.8 Reporting of Other Events

Other Reported Events are any other clinical events that are submitted by the Investigator which are not caused by or associated with the study device and/or system component(s) and/or defined as an AE.

8.2.9 Reporting of Clinical Events

All clinical events resulting in outpatient (< 24 hours) or inpatient (≥ 24 hours) hospitalizations, observational care visits, emergency room visits, urgent care center visits, or physician's office visits must be reported to the Sponsor. Detailed source documentation surrounding the clinical event should also be provided to the Sponsor. These detailed source documents may include, but are not limited to:

- Emergency department notes
- Physician consultation notes
- Medication records and logs
- Admission notes
- Laboratory results and summary details
- Discharge summary
- Operative notes
- Clinician progress notes
- X-ray and other radiological reports
- Diagnostic test reports

The applicable eCRFs should be completed for each episode of a clinical event. Supporting documentation should be submitted to the Sponsor along with the applicable eCRF.

8.2.10 Reporting Events to Participants

The DSMB will periodically review study data and will determine if any new, previously undisclosed risks should be added to the informed consent document. Should any informed consent updates be required, after approval by the relevant IRB, subjects may be asked to reconsent to the study, per local regulations.

Furthermore, any new or previously undisclosed risks will be appropriately communicated to participating Investigators.

8.2.11 Reporting of Pregnancy

If a subject becomes pregnant during participation in the study, study participation will be discontinued and documented.

9. STATISTICAL CONSIDERATIONS

A formal Statistical Analysis Plan (SAP) provides details of the statistical analyses separately.

9.1 Statistical Hypotheses

Primary Effectiveness Endpoint:

The primary effectiveness endpoint is the rate of inappropriate shock. A one-sided upper 98% confidence limit will be calculated for the inappropriate shock rate per 100 patient-months at the final analysis.

Only first inappropriate shocks will contribute the analysis of this endpoint. All wear times through the first inappropriate shock or through death or withdrawal will contribute to the Poisson regression model. All follow-up beyond the first inappropriate shock will not be used.

The formal hypotheses are:

H0: Inappropriate shock rate \geq 2.0 per 100 patient-months

Ha: Inappropriate shock rate < 2.0 per 100 patient-months.

Primary Safety Endpoint:

The primary safety endpoint is the rate of subjects experiencing a clinically significant ADE. The primary safety endpoint will use a one-sided, exact 95% upper confidence bound which will be compared to the performance goal of 15%. The hypotheses tested will be as follows:

H0: π ≥ 0.15 Ha: π < 0.15

where π is the observed proportion of subjects experiencing a clinically significant cutaneous adverse device event.

Secondary Endpoint:

The secondary endpoint of successful conversion of at least one shockable rhythm with a salvo of up to five (5) shocks will not be formally tested.

The secondary endpoints of compliance rate of subjects wearing the Jewel, and the QOL analysis will not be formally tested.

9.2 Samples Size Determination

The estimated power for the Primary Endpoint analysis is based off Monte-Carlo simulations. Assuming an average of 2.5 subject-months of wear time per subject and an expected inappropriate shock rate of 0.37 per 100 subject-month, a total of 290 subjects are required to provide approximately 98% power to demonstrate that the inappropriate shock rate is below 2.0% per 100 subject months, assuming the Type I error rate at the final analysis is 0.02. A total of up to 370 subjects may be enrolled in the study to account for 20% subject withdrawals, LTFUs, and devices that may be lost or damaged when being returned to Element Science.

Although the secondary endpoint of successful termination of life-threatening VT or VF episodes is not being formally tested, this study is designed to provide data to support this secondary endpoint. The number of shockable episodes will be monitored over the course of the trial with the goal to observe at least one (1) successful conversion of life-threatening VT or VF with a salvo of up to five (5) shocks. It is anticipated that three (3) such events will occur during this trial.

9.3 Populations for Analyses

All subjects enrolled will be evaluated on the primary and secondary endpoints. All actual wearable device times following a subject's initial Jewel placement will be included in the primary analysis. The actual wear times will be used. Data will not be imputed for endpoint calculations. A subject is considered analyzable in this population if they contribute any length of wear time with the Jewel.

A per-protocol analysis population will be defined as those subjects without major protocol deviations. Analyses on the safety and effectiveness endpoints will be repeated on this population. A subject is considered analyzable in this population if they have worn the Jewel on average for at least 14.1 hours a day.

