3.2 Endpoints

3.2.1 Primary Effectiveness Endpoint

To demonstrate an observed inappropriate shock rate of no more than 2.0 inappropriate shocks per 100 patient-months using a one-sided upper 97% confidence interval and >83% power at the interim analysis; and a 98% confidence interval and >98% power for the final analysis.

An inappropriate shock is defined as a shock delivered during a period where the study subject is not experiencing life threatening VT or VF. Only first inappropriate shocks will contribute the analysis of this endpoint. All inappropriate shocks will be reviewed and adjudicated by a Clinical Events Committee (CEC) and reported throughout the prescription period.

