4. STUDY DESIGN

4.1 Overall Design

This study is a multi-center, prospective, single-arm evaluation of the Jewel P-WCD in adult subjects at risk for sudden cardiac arrest, who are not candidates for or who refuse an implanted cardioverter defibrillator. The study will include up to sixty (60) sites in the United States. This design incorporates one interim analysis at 179 analyzable subjects and one final analysis at 290 analyzable subjects.

There is another analysis point once 100 subjects have completed their prescription wear time, which will be performed to support application for CE mark.

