9.4.4 Planned Interim Analyses

A single interim analysis will be performed after 179 or more subjects have completed their prescription wear time. This analysis will be used to stop the trial early for both safety and effectiveness. The Type I error rate for this analysis will be set to 0.03.

There is another planned analysis once 100 subjects have completed their prescription wear time, which will be performed to support application for CE mark. The data will be summarized descriptively and no formal hypothesis testing will be done at this point, so no adjustment for the Type I error rate is necessary. The results of the 100 subject interim analysis will not be used to terminate the IDE trial prior to completion of enrollment and subject follow up.

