5.1. Primary Effectiveness Endpoints

All shocks during analyzable wear time will be recorded, centrally evaluated and adjudicated by the Clinical Events Committee (CEC), and reported.

The primary effectiveness endpoint is the rate of inappropriate shock. A one-sided upper 98% confidence limit will be calculated for the inappropriate shock rate per 100 patient-months at the final analysis. Specifically, an intercept-only Poisson regression model will be fit to the data. All wear times through the first inappropriate shock or through death or withdrawal or wear times for subjects without inappropriate shock, death, or withdrawal at the time of analysis will contribute to the Poisson regression model. The one-sided upper 98% confidence limit inappropriate shock rate will be calculated by taking the one-sided upper 98% confidence limit of the intercept parameter in the regression model. The null hypothesis will be rejected if the upper confidence limit on the inappropriate shock rate is less than 2.0.

The formal hypotheses are:

 H_0 : Inappropriate shock rate ≥ 2.0 per 100 patient-months H_a : Inappropriate shock rate < 2.0 per 100 patient-months

The analysis will be re-run on the per protocol analysis population if that population is different from the primary analysis population. Results of this analysis are strictly supportive.

Note that subjects experiencing an inappropriate shock will continue to be followed and accumulate wear time in order to collect data on the other endpoints of this trial.

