5.5. Interim Analyses

An interim analysis of the Primary Endpoints will be performed after 179 subjects or more have completed their prescription wear time. This analysis will be used to stop the trial early for both safety and effectiveness.

This interim analysis will be analyzed as described in Section 5.1 above, with the exception that a one-sided upper 97% confidence bound will be used. This effectively spends 0.03 alpha on the interim analysis, reserving 0.02 alpha for the final analysis. Splitting the overall alpha into two pieces that add up to the overall alpha is a recognized way of controlling the Type I error rate. This can be seen by calculating the probability of making a Type I error. First calculate the probability of not making a Type I error which is:

Prob(no Type I in interim analysis)*Prob(no Type I in final analysis)= 0.97*0.98=0.9506

The probability of making a Type I error is then one minus the probability of not making any Type I errors which is:

Prob(Type I error)= 1.0 - 0.9506 = 0.0494

This particular split in alpha also corresponds to using a cumulative error spending function of Jennison and Turnbull (2000) defined as:

$$E(t,\rho) = \begin{cases} 1 & if \quad t \ge 1 \\ t^{\rho} & if \ 0 < t < 1 \\ 0 & otherwise \end{cases}$$

where ρ is the power parameter (here ρ =1.059) and t is the information fraction at the time of the interim analysis (here t = 179/290). Given these values, the amount of alpha spent at the interim analysis is:

 $\alpha^* E(179/290, 1.059) = 0.05^*(179/290)^{1.059} = 0.02999$

The safety endpoint will also be tested at this interim analysis only if the primary effectiveness endpoint is achieved. The trial will only be stopped if both the primary effectiveness and primary safety endpoints are achieved.

There is another planned analysis when 100 subjects have completed their prescription wear time, which will be performed to support application for CE mark. The data will be summarized descriptively and no formal hypothesis testing will be done at this point, so no adjustment for Type I error rate is necessary. Once discussions with the Notified Body are concluded, this document will be updated with details regarding the analysis.

6. Handling of Missing Data

It is expected that most subjects will wear the device between 40 and 90 days. Subjects with missing wear times will not have their data imputed for the purpose of the primary endpoint analysis.

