For the purposes of sample size calculation, the expected inappropriate shock rate was set to 0.37 shocks per 100 subject-months. This is the inappropriate shock rate observed in the NEJM published LifeVest "VEST" RCT² and it is assumed that the Jewel P-WCD will have a similar or better inappropriate shock rate. Assuming an expected inappropriate shock rate of 0.37 per 100 subject-month, a total of 290 subjects are required to provide approximately 98% power to demonstrate that the inappropriate shock rate is below 2.0% per 100 subject-months. For purposes of sample size calculation, the Type I error rate was set at 0.02 and it was assumed that the subjects had a 2.5-month average prescription wear time.

Sample sizes required to test the primary safety endpoint were lower than those needed for the effectiveness endpoint, so the sample size needed for effectiveness was chosen as the overall sample size.

A site enrollment cap of 20% will be employed in order to ensure no one site dominates enrollment in this trial.

The study is designed to provide data to support the secondary endpoint of demonstration of successful conversion of life-threatening VT or VF episodes. The number of shockable episodes will be monitored over the course of the trial with the goal to observe at least one (1) successful conversion of life-threatening VT or VF with a salvo of up to five (5) shocks.

In order to adjust for a 20% early withdrawal and/or loss to follow-up subjects, a total enrollment of 290/0.80 = 363 subjects may be needed.

9. Poolability Assessment

Site poolability will be assessed using an Rx2 table where each site is a row in the table and the two columns are "number of subjects experiencing an inappropriate shock" and "number of subjects free from inappropriate shocks." Noting that each site had an enrollment cap of approximately 20%, an attempt will be made to test for poolability using a standard Pearson chi-square statistic, however, due to the low probability of receiving an inappropriate shock and the enrollment cap, the table may have many sampling zeros making the Person chi-square statistic invalid. If the standard asymptotic Pearson chi-square test is not valid, exact methods will be used for comparing the sites. A p-value less than 0.15 will indicate that the sites are not poolable and that adjustments for site must be made in the primary endpoint analysis.

10.Sub-group Analyses

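### Power rests on patient-months, but the final look is set by a head-count that early withdrawers can fill; the interim trigger is stated two ways

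*Protocol*

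**What the plan says.** Protocol 4.1 plans "one interim analysis at 179 analyzable subjects and one final analysis at 290 analyzable subjects". For the main population, Protocol 9.3 states: "A subject is considered analyzable in this population if they contribute any length of wear time with the Jewel". Protocol 7.2 says that subjects who are enrolled and later withdrawn are not replaced. Their wear up to withdrawal enters the model (Protocol 9.1, SAP 5.1).

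The interim has a second trigger. Protocol 9.4.4 places it "after 179 or more subjects have completed their prescription wear time", and SAP sections 2 and 5.5 also use completed prescription wear.

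On power, Protocol 3.2.1 claims ">83% power at the interim analysis" and above 98% at the final analysis, while Protocol 9.2 and SAP section 8 say about 98% for 290 subjects. SAP section 8 draws each subject's wear from a normal distribution with mean 2.5 months and SD 0.5. It describes no withdrawal component and adds that "it was assumed that the subjects had a 2.5-month average prescription wear time".

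On attrition, Protocol 9.2 says: "A total of up to 370 subjects may be enrolled in the study to account for 20% subject withdrawals, LTFUs", and also names lost or damaged devices. SAP section 8 computes 290/0.80 = 363.

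**The concern.** In an intercept-only Poisson model the precision of the rate depends on events and total exposure. A subject who leaves after two days adds one to the head-count and almost nothing to the information. Because any wear makes a subject analyzable, such subjects can occupy places among the 290. Neither document requires enrolment to go on toward 363 or 370 once 290 are analyzable, and neither sets a minimum total exposure. The 20% allowance therefore protects the power only if the sponsor chooses to use it for that purpose.

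What is at stake is whether the trial has the power it states. At the interim there is also the 0.03 of alpha, which is spent whether or not the look had enough exposure to succeed.

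**Working it through.** **Inputs.** Goal 2.0 per 100 patient-months, i.e. 0.02 per month (SAP 5.1: "The null hypothesis will be rejected if the upper confidence limit on the inappropriate shock rate is less than 2.0"). True rate 0.37 per 100, i.e. 0.0037 per month (SAP 8). One-sided alpha 0.03 interim and 0.02 final (SAP 5.5). Wear N(2.5, 0.5) months, and 0.5 events substituted when a simulated trial has none (SAP 8). Withdrawal 20% (Protocol 9.2, SAP 8). The timing of withdrawal is my assumption.

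**Test.** With d events in T patient-months, the regression upper limit is U = (d/T)·exp(z/√d), with z = 2.054 at 98% and 1.881 at 97%. Success means U < 0.02, so d events pass only if T > d·exp(z/√d)/0.02.

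- Final: 4 events need 558 patient-months, 5 need 626 and 6 need 694.
- Interim: 0 events (as 0.5) need 357, 1 needs 328, 2 need 378 and 3 need 444.

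**Reproducing the plan.** 290 × 2.5 = 725, so up to 6 events pass. Expected events are 725 × 0.0037 = 2.68, and P(6 or fewer) = 98.0%. Simulation as in SAP section 8 (40,000 trials, time counted to first shock) gives 98.0–98.1% at the final look. With 179 × 2.5 = 447.5 at the interim it gives about 83.7%. Both stated figures reproduce.

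**20% withdrawals inside the head-count.** At the final look, 232 subjects have full wear and 58 withdraw. At the interim under Protocol 4.1 the numbers are 143 and 36. Nominal exposure for half-way leaving is 290 × 2.5 × 0.9 = 652.5, and for leaving at once 290 × 2.5 × 0.8 = 580. Stopping the clock at a first shock lowers these slightly.

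| Scenario | Final: months, power | Interim (Protocol 4.1): months, power |
|---|---|---|
| As planned | 725, 98% | 447.5, 84% |
| 20% leave half-way or at a uniform time | about 650, 96% | about 401, 81–82% |
| 20% leave almost at once | about 577, 93% | about 357, 50% |

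The 50% arises because about 357 patient-months is exactly where a zero-event trial begins to pass under the 0.5-event substitution. With an exact Poisson limit it is about 81%.

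**Completer trigger (Protocol 9.4.4, SAP 5.5).** 179 completers plus 45 withdrawers leaving at uniform times give about 501 patient-months and 88.5% interim power. Withdrawal does not erode the stated figure.

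**Shorter wear.** SAP section 6 says: "It is expected that most subjects will wear the device between 40 and 90 days". Taking the midpoint of 65 days as the mean (an assumption; 65/30.44 = 2.14 months, SD 0.5) gives about 617 and 381 patient-months, with 92% final and 74% interim power. With an exact limit these are about 97% and 83%. This loss applies under either interim trigger.

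**If the allowance is used.** 290 full-wear subjects plus 73 uniform withdrawers (363 enrolled) give about 813 patient-months and 98.9%. With 370 enrolled and 20% contributing nothing, exposure is 370 × 0.8 × 2.5 = 740 before stopping the clock at first shocks, and power is about 98%.

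**The case against.** A head-count trigger is a legitimate choice, and at the final look the loss is small. A missed interim only continues the trial. Both stand, and they limit the weight of the point.

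Several stronger readings are tempting but not supported:

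- **That the 20% allowance achieves nothing.** It expressly covers lost or damaged devices; a subject with no usable device data has no analyzable wear under SAP 3.1 and does not fill a place. Nothing stops enrolment at 290 either, and enrolling 363 to 370 keeps the power.
- **That withdrawal erodes both looks.** This follows only from Protocol 4.1. The sections devoted to the interim count completers.
- **That power should be cut for wear of 14.1 hours a day.** That figure is a threshold to exceed and the per-protocol minimum, not a forecast. SAP 5.4 describes prescription wear time as already net of removals and missing data, although its formula then subtracts gaps again. The 2.5 months may therefore already be on-body time.
- **That 2.5 months is implausible because wear ends at 90 days.** The documents say that most subjects fall in that range. Protocol 2.1 and SAP section 1 allow longer, and participation may run to 180 days.
- **That a look with little exposure cannot succeed at any event count.** This depends on the 0.5-event substitution, which SAP section 8 states for the simulations; SAP 5.1 does not state it for the analysis.

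**Conclusion.** The point holds in limited form. The stated power is correct at 725 and 447.5 patient-months, but the plan does not secure those amounts. With its own 20% withdrawals inside the 290, final power is about 93–96% instead of 98%. At the interim the effect depends on which trigger governs: about 82% down to 50% under Protocol 4.1 (81% at the low end with an exact limit), and no loss from withdrawal under the completer rule. Prescriptions averaging less than 2.5 months would lower power under either trigger.

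Type I error is not affected by this point. The sizes rest on the assumed timing of withdrawal, the 0.37 rate and, for the shorter-wear case, the 65-day mean. Power moves in steps because events are whole numbers: 620 patient-months gives about 92%, slightly less than 577. The figures should therefore be read as levels, not as a smooth curve.

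**What to change.** 1. Run the interim when at least 179 subjects have completed prescription wear **and** at least 447.5 analyzable patient-months have accrued.
2. Run the final analysis when there are at least 290 analyzable subjects **and** at least 725 analyzable patient-months, within the existing ceiling of 370 enrolled. State that enrolment continues toward that ceiling until the exposure is reached.
3. Make Protocol 4.1 agree with Protocol 9.4.4 and SAP sections 2 and 5.5 on the interim trigger.
4. State final power as conditional on exposure: about 98% at 725 patient-months, 96% at 650 and 93% at 577. If the ceiling is reached first, report the power at the exposure achieved.

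The planned information fraction is unchanged (447.5/725 = 179/290 = 0.617), and the 0.03/0.02 split stands.

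The cost is protocol and SAP wording, enrolment that may run closer to the 370 already allowed, and looks that may come slightly later. The ceiling is not a guarantee. With a 65-day mean and 20% leaving half-way, 370 subjects give about 370 × 2.136 × 0.9 = 711 patient-months, just short of 725, which is why the last sentence of item 4 is needed.
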